### Major Hemorrhage

Adhering to published guidelines, the criteria of major hemorrhage in non-surgical participants is:[30]

- Fatal bleeding, and/or
- Symptomatic bleeding in a critical area or organ such as intracranial, intraspinal, intraocular, retroperitoneal, intra-articular or pericardial, or intramuscular with compartment syndrome, and/or
- Bleeding causing a fall in hemoglobin level  $\geq 2$  g/L or
- Bleeding leading to a transfusion of  $\geq 2$  units of packed red blood cells.

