## 2.4 Correlative Studies Background

**Evaluation of Padua, IMPROVE, and Khorana risk models in hospitalized cancer patients.** Published risk models have been developed to identify a collective group of risk factors that identify patient populations considered to be at sufficiently high risk of thrombosis to warrant thromboprophylaxis. The IMPROVE scoring model was developed using a database of 15,000 patients from 12 countries. A multiple regression analysis identified independent risk factors for VTE in acutely ill hospitalized medical patients.[15] The incidence of thrombosis following hospitalization was 11% in patients with IMPROVE scores  $\geq 5$ . The four independent risk factors at admission comprising the scoring model are: previous history of VTE (3 points), known thrombophilia (3 points), age  $> 60$  years (1 point), and cancer (1 point). The Khorana score was developed for cancer outpatients receiving chemotherapy. Abnormal pre-chemotherapy complete blood count indices (white blood cell  $> 11 \times 10^9/L$ , hemoglobin  $< 10 \text{ g/dL}$ , and/or platelet count  $> 350 \times 10^9/L$ ) are independently associated with thrombosis in cancer outpatients and are elements of the Khorana risk score.[16-18] In order to evaluate the performance of the Khorana score in predicting thrombotic risk for hospitalized cancer patients, we will calculate the Khorana score utilizing laboratory data (e.g. blood counts) upon admission. The Khorana score will be calculated for all patients following completion of the study during the data analysis phase. As this scoring system was not specifically developed for cancer patients, we will explore whether improved specificity can be achieved while retaining sensitivity to identify patients at greatest risk for VTE.

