#### **5.6 Criteria for Taking a Participant Off Protocol Therapy**

Cessation of enoxaparin and withdrawal from the study is mandated for the following reasons:

- Grade 3 or 4 hemorrhage and/or
  - Symptomatic hemorrhage in a critical area or organ such as intracranial, intraspinal, intraocular, retroperitoneal, intra-articular or pericardial, or intramuscular with compartment syndrome, and/or hemorrhage causing an acute fall in hemoglobin  $\geq 2\text{g/L}$  or hemorrhage leading to a transfusion of  $\geq 2$  units of packed red blood cells.
- Development of confirmed heparin induced thrombocytopenia
- Proximal deep vein thrombosis or pulmonary embolism
- Condition requiring therapeutic anticoagulation or dual antiplatelet therapy
- Renal failure (see section 6)
- Participant decides to withdraw from the protocol therapy
- General or specific changes in the participant's condition render the participant unacceptable for further treatment in the judgment of the treating investigator

Participants will be removed from the protocol therapy when any of these criteria apply. The reason for removal from protocol therapy, and the date the participant was removed, must be documented in the case report form (CRF). Alternative care options will be discussed with the participant.

A QACT Treatment Ended/Off Study Form will be filled out when a participant is removed from protocol therapy. This form can be found on the QACT website or obtained from the QACT registration staff.

In the event of unusual or life-threatening complications, treating investigators must immediately notify the Overall PI:

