### Hemorrhage

Hemorrhage	Management/Next Dose for  Arm A (standard enoxaparin)	Management/Next Dose for  Arm B (adjusted dose enoxaparin)
$\leq$ Grade 1	No change in dose	No change in dose
Grade 2	Hold* until $\leq$ Grade 1. Resume at same dose.	Hold* until $\leq$ Grade 1. Resume at same dose level.
Grade 3	Discontinue (off protocol therapy)	Discontinue (off protocol therapy)
Grade 4	Discontinue (off protocol therapy)	Discontinue (off protocol therapy)

\*Participants requiring a delay of  $> 3$  days should go off protocol therapy.

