### **Major hemorrhage:**

An independent adjudication committee of three hematologists will review all details of hemorrhagic events in a blinded manner to determine whether event met criteria for major hemorrhage. Any disagreements will be settled by majority consensus.

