#### **13.2 Sample Size, Accrual Rate and Study Duration**

The documented incidence of VTE in cancer patients in randomized clinical trials ranges considerably (3-17%) on pharmacologic thromboprophylaxis at standard prophylactic dosing.[8] With the additional incorporation of tumor-specific thrombotic risk assessment, we anticipate the incidence of VTE for high risk cancer patients receiving fixed standard dose enoxaparin will be greater than 10%, especially with inclusion of protocol-mandated lower extremity ultrasounds.

We plan to enroll a total of 50 high risk cancer patients between Beth Israel Deaconess Medical Center and Cleveland Clinic Foundation, of which 25 will be randomized to standard dose enoxaparin. Assuming a cumulative incidence of thrombosis at day 17 is 12% (90% binomial confidence interval 3.3 to 28.2%), While we anticipate an increased risk of major hemorrhage observed in cancer patients compared to that of general medical patients, we expect these events to be rare. Point estimates of hemorrhage endpoints at Day 14 will be provided along with the 90% exact binomial confidence intervals. The point estimate will serve to inform sample size calculations for a larger phase III clinical trial.

The trial will only be open at BIDMC and Cleveland Clinic and we anticipate enrolling 3 patients per month.

Participants who receive at least one dose of treatment post-randomization will be considered evaluable for the study.

Accrual Targets				
Ethnic Category	Sex/Gender			
	Females		Males	
Hispanic or Latino	13	+	12	= 25
Not Hispanic or Latino	12	+	13	= 25
Ethnic Category: Total of all subjects	25 (A1)	+	25 (B1)	= 50 (C1)
Racial Category				
American Indian or Alaskan Native		+		=
Asian	3	+	2	= 5
Black or African American	5	+	6	= 11
Native Hawaiian or other Pacific Islander		+		=
White	17	+	17	= 34
Racial Category: Total of all subjects	25 (A2)	+	25 (B2)	= 50 (C2)
	(A1 = A2)		(B1 = B2)	
			(C1 = C2)	

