### 13.5 Analysis of Primary Endpoints

Cumulative incidence of VTE at day 17 (in arm A) and major hemorrhage endpoints at day 14 (both arms) will be calculated along with their 90% exact binomial confidence intervals.

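### The primary major-hemorrhage endpoint counts a hemoglobin fall of 2 g/L (0.2 g/dL), probably a unit error, which must be checked before any event is adjudicated

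*Combined protocol and SAP*

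**What the plan says.** Section 11 (Major Hemorrhage) gives four alternative criteria, any one of which is enough, and says they follow a published guideline (reference 30). They are:

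- fatal bleeding;
- symptomatic bleeding in a critical area or organ;
- "Bleeding causing a fall in hemoglobin level" of at least 2 g/L;
- "Bleeding leading to a transfusion of" at least 2 units of packed red cells.

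Under Response Review in the same section, three hematologists review hemorrhagic events blinded, "to determine whether event met criteria for major hemorrhage".

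The endpoint is primary. Section 13.5 says that "major hemorrhage endpoints at day 14 (both arms) will be calculated along with their 90% exact binomial confidence intervals". Section 13.2 says of major hemorrhage that "we expect these events to be rare" and that the point estimate will inform the sample size of a phase III trial.

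Section 5.6, on coming off protocol therapy, repeats the 2 g/L figure but words it as "hemorrhage causing an acute fall in hemoglobin".

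**The concern.** A fall of 2 g/L is 0.2 g/dL. That is a very small change to place beside death, intracranial bleeding or a two-unit transfusion as an equally sufficient sign of major hemorrhage. The likeliest explanation is that g/L was written where another unit was meant.

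The wording decides what counts as a primary event. Applied literally, a confirmed minor bleed with a very small attributable fall in hemoglobin would count as major. With 25 patients per arm, a few such events would dominate the hemorrhage estimate in either arm, and that estimate would then be carried into the phase III planning.

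**Working it through.** **Inputs.**
- Threshold: 2 g/L (section 11, Major Hemorrhage; repeated in section 5.6).
- The only other hemoglobin figure in the documents: below 10 g/dL, among the "Abnormal pre-chemotherapy complete blood count indices" in section 2.4.
- Patients: 50 in total, 25 of them on standard dose (section 13.2); section 13.4 uses 25 for Arm B.
- Hemorrhage rate: 2%, stated as a conditional (section 13.4).
- Interval: 90% exact binomial (section 13.5).

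**1. The plan's own figure.** Section 13.4 gives 0.09 as the probability of 2 or more hemorrhages in 25 patients at a true rate of 2%.

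P(X ≥ 2) = 1 − 0.98^25 − 25 × 0.02 × 0.98^24 = 1 − 0.6035 − 0.3079 = 0.0886.

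The figure reproduces. It depends only on the assumed rate, so correcting the unit would not change it. The problem is in what is counted, not in this calculation.

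**2. Conversion.** 2 g/L ÷ 10 = 0.2 g/dL. Against 10 g/dL, 0.2 ÷ 10 = 2%. The same number in g/dL would be 20 g/L, ten times as large.

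**3. Does 0.2 g/dL fit the rest of the plan?**
- The other three criteria in section 11 all describe serious bleeding.
- Section 13.2 expects rare events and section 13.4 works with 2%. Section 2.2 cites 6/360 = 1.7% on enoxaparin 40 mg and 4/362 = 1.1% on placebo, and section 7.2.1 cites a rate below 1%.
- Section 2.4 gives hemoglobin in g/dL.
- No section explains or justifies a 2 g/L threshold, and none gives 2 g/dL or 20 g/L.

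The g/L unit stands in both section 11 and section 5.6, so a one-off fault in reading the PDF is unlikely.

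**4. Sensitivity of the estimate.** One event in 25 is 1/25 = 4%. Clopper-Pearson 90% intervals:

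| Events in 25 | Estimate | 90% exact interval |
|---|---|---|
| 0 | 0% | 0 to 11.3% |
| 1 | 4% | 0.2 to 17.6% |
| 2 | 8% | 1.4 to 23.1% |

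**5. Illustration, by assumption only.** The documents do not give the frequency of lesser bleeds or of small attributable falls. Take a true major rate of 2%, lesser bleeds in 5% to 20% of patients, and 25% to 100% of those meeting the literal rule:

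- low end: 0.02 + 0.05 × 0.25 = 0.0325, or 3.25%; × 25 = 0.8 expected events;
- high end: 0.02 + 0.20 × 1.00 = 0.22, or 22%; × 25 = 5.5 expected events;
- without reclassification: 0.02 × 25 = 0.5 expected events.

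**6. Section 5.6 against sections 11 and 6.** Section 5.6 requires the fall to be acute; section 11 does not. Section 5.6 also applies its hemoglobin and transfusion criteria regardless of grade and mandates cessation. The hemorrhage table in section 6 acts by grade: no change up to Grade 1, and a hold followed by resumption at Grade 2 (for Arm B, "Resume at same dose level"). A bleed of Grade 2 or below with a 2 g/L fall therefore falls under conflicting instructions.

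**The case against.** The strongest reply is that the unit error is inferred. Both places that state the criterion agree on g/L, and the cited guideline is not available here. The g/dL figure in section 2.4 belongs to a different score, and the expectation of rare events was not derived from the threshold. This stands as a limit on certainty: the literal threshold is clearly out of scale, but that the unit is wrong is only likely.

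The second reply is that few trivial falls would reach the count. Bleeding must cause the fall, and blinded hematologists review each event. Under section 7.1 an abnormal laboratory value alone is not an adverse event unless it has clinical consequences. The study calendar schedules blood counts only at screening, day 1 and day 7, with day 7 optional after discharge, though routine care may add others. These points limit the inflation but do not remove the defect. The committee decides whether an event met the written criteria, and the only written hemoglobin criterion is 0.2 g/dL. If it applies that figure, minor bleeds can count as major; if it quietly applies another, the endpoint analyzed is not the one specified.

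Third, the 4-point steps hold for any binary endpoint with 25 patients, and the 3.25% to 22% range rests on assumed inputs. Both are true. The steps show how sensitive the estimate is, the range is only an illustration, and the conclusion does not depend on it.

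Finally, an endpoint and an off-therapy rule need not share wording, and the missing time window and reference hemoglobin are matters of detail. That is fair; neither carries weight in the conclusion.

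**Conclusion.** The concern holds. A primary endpoint in both arms is defined partly by a hemoglobin fall of 0.2 g/dL, which is out of scale with its companion criteria and with the plan's expectation of rare events. A unit error is the likely cause; proof needs reference 30.

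Each event wrongly counted adds 4 percentage points to an arm's estimate. The number of such events cannot be derived from the documents. The range of 0.8 to 5.5 expected events per 25 patients, instead of 0.5, rests wholly on the assumptions in the working. No figure stated in the plan is numerically wrong because of this, and the sample size is unaffected. Because the definition determines which bleeds enter a primary result, it must be settled before adjudication begins.

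**What to change.** 1. Check the hemoglobin criterion in section 11 against reference 30, correct the unit, and state the threshold in both g/dL and g/L.
2. While the text is open, add the time window for the fall and say which hemoglobin value is the reference. The study calendar records admission, screening and day 1 counts, and none is named as baseline.
3. Give the adjudication committee the corrected text before it reviews any event.
4. Separately, have the investigators reconcile the same figure in section 5.6 with section 11 and with the hemorrhage table in section 6. Which clinical rule applies there is theirs to decide; it should not be changed automatically along with the endpoint.

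The cost is a check of one cited source, a short text correction and a note to the committee. No patients or procedures are added.

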### **Response Review**

**VTE:** A blinded-centralized independent adjudication of VTE qualifying for the primary outcome will be performed at BIDMC. The review committee will be comprised of two independent radiologists who will review all lower extremity ultrasounds as well as any other imaging that identifies a new thromboembolism. Any disagreements will be settled by consensus.

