### **5. TREATMENT PLAN**

#### **5.1 Treatment Regimen**

##### **Treatment Overview:**

Eligible participants will be randomized to standard dose enoxaparin at 40 mg once daily (Arm A) versus weight-based enoxaparin at 1 mg/kg once daily (Arm B). On study enoxaparin will be administered for up to 14 days during hospitalization. Physicians and participants will be double-blinded to enoxaparin dosing during hospitalization (or up to 14 days). After the day 14 assessment, treatment arms will be un-blinded in order to appropriately schedule a bilateral lower extremity ultrasound for participants enrolled onto Arm A at day 17.

Note that patients who are discharged and re-admitted prior to day 14 will resume study procedures and enoxaparin administration per initial randomization.

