## 11. MEASUREMENT OF EFFECT

### Venous Thromboembolism (VTE)

Cumulative incidence of venous thromboembolic events is the primary endpoint for Arm A and a secondary endpoint for Arm B. ***The composite endpoint includes objectively confirmed proximal or distal lower extremity DVT, subsegmental or larger pulmonary embolism; or fatal PE diagnosed by autopsy.*** All other venous or arterial events will be recorded and analyzed as secondary endpoints (including central line associated DVT).

Participants presenting with symptoms compatible with DVT and/or PE will undergo radiographic imaging with compression ultrasound, VQ lung scan, or spiral CT. Confirmed episodes of VTE will be managed by the treating physician per standard of practice.

Presence of any of the following will be considered diagnostic for a VTE:

- New non-compressibility of lower extremity deep venous segments by compression ultrasound.
- Intraluminal defects in two or more views on pulmonary angiography
- Sudden contrast cut-off of one or more vessels greater than 2.5 mm in diameter on a pulmonary angiogram
- A high probability VQ lung scan showing one or more segmental perfusion defects with corresponding normal ventilation (mismatch defect)
- Abnormal spiral CT showing thrombus in pulmonary vessels (subsegmental or larger)

Those VTE that do not qualify for the primary endpoint such as a central line-associated thrombus will be recorded and analyzed as secondary endpoints.

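### Central review of VTE checks the pulmonary embolism component in one direction only: a positive chest scan can be overturned, but a negative one is never re-read

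*Combined protocol and SAP*

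**What the plan says.** Section 11 (Venous Thromboembolism) sets the endpoint by arm: "Cumulative incidence of venous thromboembolic events is the primary endpoint for Arm A and a secondary endpoint for Arm B". The qualifying events are "proximal or distal lower extremity DVT, subsegmental or larger pulmonary embolism; or fatal PE diagnosed by autopsy". Imaging is triggered by symptoms: "Participants presenting with symptoms compatible with DVT and/or PE will undergo radiographic imaging with compression ultrasound, VQ lung scan, or spiral CT". The diagnostic criteria in the same section also admit pulmonary angiography.

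Sections 5.1 and 5.3 add a screening scan for asymptomatic DVT in one arm only; staff are to "schedule a bilateral lower extremity ultrasound for participants enrolled onto Arm A at day 17".

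Under Response Review, the adjudication is described as follows: "A blinded-centralized independent adjudication of VTE qualifying for the primary outcome will be performed at BIDMC". The committee is two independent radiologists "who will review all lower extremity ultrasounds as well as any other imaging that identifies a new thromboembolism", with disagreements settled by consensus.

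Sections 13.2 and 13.5 give the use of the result: a day-17 VTE rate in 25 Arm A participants with an exact 90% interval, intended to inform the size of a phase III trial.

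**The concern.** The sentence on what the radiologists see contains two selection rules. Leg ultrasounds go to review regardless of result. All other imaging goes only if it has already shown a new thromboembolism. A CT, VQ scan or angiogram done for suspected PE and reported negative has no route to the committee.

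For DVT, then, central review can correct both false positives and false negatives. For PE it can correct only false positives. Missed PEs stay missed, so one component of the composite is verified to a lower standard than the other. Subsegmental emboli count, so small findings on chest imaging matter to the endpoint.

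There is a second, lesser effect. Any chest scan that reaches the committee is known to have been called positive, because that is why it was sent. Blinding to the earlier read is thus weaker for PE than for ultrasound.

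What is at stake is the accuracy of a point estimate that is the trial's main product. The exact binomial interval describes sampling error and does not allow for events that were never ascertained.

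**Working it through.** **Step 1. The plan's own figure.** Inputs from section 13.2: n = 25 in Arm A, assumed rate 12%, so x = 3. The exact (Clopper-Pearson) 90% limits are the 5% quantile of Beta(x, n − x + 1) and the 95% quantile of Beta(x + 1, n − x). For 3/25 these are 3.35% and 28.17%. The stated 3.3 to 28.2% is reproduced within rounding.

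**Step 2. Which corrections the review rule allows.**

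| Component | Positive site read re-read? | Negative site read re-read? | Possible effect of review |
|---|---|---|---|
| Leg DVT on ultrasound | Yes | Yes | Remove or add an event |
| PE on CT, VQ or angiography | Yes | No | Remove an event only |

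**Step 3. What one event is worth.** 1/25 = 4 percentage points. Starting from 3/25:

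- One PE overturned, in a participant with no other qualifying event: 2/25 = 8% (exact 90% interval 1.4 to 23.1%).
- One DVT added on re-reading an ultrasound: 4/25 = 16% (5.7 to 33.0%).

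So the composite can move either way. The documents give neither the expected split between DVT and PE nor any reader error rate, so the net movement cannot be computed.

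**Step 4. Expected number of missed PEs.** Assumptions, none of them from the documents: 3 to 5 Arm A participants have a chest scan for suspected PE that is read locally as negative; 5 to 10% of those scans contain a PE; and none of these participants has another qualifying event.

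- Low end: 3 × 0.05 = 0.15 events; 0.15/25 = 0.6 points.
- High end: 5 × 0.10 = 0.5 events; 0.5/25 = 2.0 points.

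The planned interval is 28.2 − 3.3 = 24.9 points wide. Even the high end is 2.0/24.9, about 8% of that width.

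**Step 5. The comparison in 13.6.1.** The same review rule applies to both arms. If a fraction m of true PEs is missed in each arm, the observed PE risks are (1 − m)pA and (1 − m)pB. Their ratio is unchanged and their difference shrinks by the factor (1 − m). A bias favouring one arm would need m to differ by arm, and nothing in the documents suggests that it does.

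**The case against.** The strongest answer is that the effect is small and rests on assumed inputs. That stands. The expected under-count is below one participant, the interval is about 25 points wide, and section 13.4 says that the aim is point estimates for planning a larger trial, not a powered comparison. Section 13.2 also names the mandated ultrasounds as a reason to expect a rate above 10%, and that component is fully re-read.

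Several stronger readings are tempting, and the documents do not support them:

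- A reader might infer that adjudication can only lower the primary VTE rate. It cannot be put that way, because the same sentence sends every leg ultrasound to review and a missed DVT can be added.
- A reader might count each overturned PE as a further loss with nothing to balance it. Removing a false-positive PE is a correction, not a bias, and an added DVT can offset it in the total.
- A reader might infer a bias between arms in 13.6.1. That analysis uses symptomatic events collected before unblinding, so the Arm A screening ultrasound does not enter it and the two-way DVT check offers less offset there. But the rule is the same in both arms and review is blinded, so no differential mechanism is shown.
- A reader might infer that fatal PE found at autopsy is shut out. Section 11 makes it a qualifying event in its own right, and the opening sentence on adjudication covers all VTE that qualifies for the primary outcome. How autopsy reports reach adjudication could be clarified, but this is not an error.

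The wording also does not say who identifies the thromboembolism. A reading at the site is the natural sense but is not stated. If central identification was meant, all scans would have to be sent, and the text should say so.

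**Conclusion.** The point holds for the PE component alone. On the plain reading of the review rule, a PE missed locally on CT, VQ or angiography cannot be recovered, while one read locally can be overturned. After adjudication the PE component can therefore err low from missed reads, and PE and DVT are verified to different standards within one composite.

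The direction of any net error in the full composite is unknown. The size for PE, 0.6 to 2 points on the Arm A rate, depends wholly on the assumed number of negative scans and the assumed miss rate. It would not change the use made of a 25-participant estimate. Severity is minor. The change is worth making because it replaces a selection rule that depends on the result with one that does not, for part of a primary endpoint, at very little cost.

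**What to change.** Amend the VTE paragraph under Response Review in section 11 so that the same two radiologists review, blinded to treatment arm and to the local read:

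- all leg ultrasounds, as now;
- all CT, VQ and angiography done for suspected PE, whatever the local result;
- any other imaging that reports a new thrombus.

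This also settles who does the identifying. The cost is one sentence and a handful of extra reads across 50 participants. It needs no new scans, visits or staff, and no change in sample size, since section 11 already requires imaging when symptoms arise.
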